## Fructose metabolism in the liver

High fructose diets have been shown to induce insulin resistance and hypertriglyceridemia in several animal models. It should be recognized that the liver is the major site of fructose metabolism. Importantly the metabolism of fructose differs fundamentally from that of glucose (Figure 2). The metabolism of fructose by fructokinase results in the release of three-carbon molecules substrates for DNL which are utilized for the synthesis of glycerol and free fatty acids. In contrast to glucose metabolism, fructose conversion to three carbon molecules occurs independently of regulation by insulin and there is no negative feedback via cell energy status to control this pathway resulting in increased DNL and consequently VLDL synthesis and secretion.

Insulin action in the liver involves insulin receptor kinase which phosphorylates insulin receptor substrate-1 (IRS1) and IRS2 resulting in activation of PI3K (phosphatidylinositol 3-kinase) and the protein-serine/threonine kinases Akt2. Activation of Akt2 enhances glycogen synthesis and inhibits gluconeogenesis. Defects in insulin signaling cascades have been observed in animal models on high fructose diet including increased activity of protein tyrosine phosphatase 1B (PTP-1B), phosphatase and tensin homolog deleted on chromosome ten (PTEN), SH2 domain-containing inositol phosphatase (SHIP2) and c-Jun amino terminal kinase (JNK1) resulting in hepatic insulin resistance.

**Fig 2. Metabolic pathways of fructose and glucose in the liver**

[figure not shown]
## High fructose feeding and DNL

The available evidence that fructose increases DNL from animal models in particular from fructose fed golden hamster are plenty and convincing. The key question is whether fructose consumption increases DNL *in vivo* in man to the extent that is reflected in significant excess liver fat accumulation and VLDL overproduction resulting in atherogenic dyslipidemia and increased CVD risk. Presently, scientific evidence is limited because of small studies with short follow-up periods. Acute oral fructose load increased DNL in healthy men but not in women in one recent study. The recent data by Parks *et al.* confirmed that acute consumption of fructose enhanced lipogenesis and increased postprandial TG levels. In contrast, the contribution of newly synthesized fatty acids to VLDL-TG remained minimal after acute fructose load despite increases of postprandial TG levels in another study. A short term high fructose feeding (3 g/kg BW corresponding to 800-1000 extra calories per day) on top of isocaloric diet in lean healthy men increased hepatic DNL by six-fold and fasting triglycerides by 80%. Recently Stanhope *et al.* reported that fructose -sweetened beverages providing 25 % of daily energy intake over 10 weeks increased significantly DNL and postprandial TG response but not fasting TG levels. Subjects consuming fructose exhibited significant increase in visceral fat but no changes was seen in control subjects consuming glucose. Notably, both groups showed a small but significant weight gain. Fructose consumption, but not glucose consumption, was associated with significant decrease of insulin sensitivity and increases of fasting glucose and insulin levels. Overfeeding of fructose on top of isocaloric diet over 7 days lead to increased liver fat in healthy lean men. So far this is the only study suggesting that fructose may enhance fat deposition in the liver. However, it is still unknown whether this is due to calorie excess or fructose per se. **In summary, acute fructose consumption in quantities similar to average American daily fructose intake stimulate DNL and enhance postprandial lipemia. The effect of chronic fructose intake and the direct contribution of DNL to liver fat, VLDL production and postprandial TG kinetics are not established in humans and research in this area is urgently needed.**

## Fructose and inflammation

Recently, fructose feeding has been reported to activate inflammatory pathways (Figure 3). Fructose feeding in rats is associated with increased inflammatory proteins and markers of oxidative stress. In two animal models fructose feeding was associated with increase of tumor necrosis factor  $\alpha$  (TNF $\alpha$ ) levels in plasma associated with activation of the proinflammatory transcription factor NF- $\kappa$ B. Interestingly, TNF $\alpha$  has been reported to stimulate hepatic VLDL apo-B production accompanied by increases of MTP and hepatic insulin resistance.

Accumulation of TG in the liver leads to increased synthesis of the proinflammatory lipid family ceramide and reactive oxygen species (ROS) generation. Recently, fructose has been reported to increase ceramide concentration. In the liver accumulation of diacylglycerol (DAG) and generation of ROS activates protein kinase C delta (PKC- $\delta$ ), I $\kappa$ B kinase (IKK- $\beta$ ) and NF- $\kappa$ B pathways. IKK- $\beta$  seems to act as a mediator of TNF $\alpha$  induced insulin resistance IKK- $\beta$  activation results in increased expression of sterol regulatory element-binding protein 1 (SREBP-1) and induction of DNL. Increased NF- $\kappa$ B activation promotes JNK-1 activation via inhibition of serine phosphorylation of IRS-1 resulting in defective insulin signaling and insulin resistance. Fructose has been also reported directly to activate JNK-1.

Given that fructose induces hepatic lipogenesis and associates with inflammatory processes it is plausible that these mechanism act in concert to further aggravate the lipogenesis pathway. To the best of our knowledge no data exist on markers of inflammation and oxidative stress in man during fructose feeding.

**Fig 3. Consequences of high fructose diet on lipid metabolism in the liver.**

## Specific Aims

[figure not shown]
Our hypothesis is that consumption of fructose-containing beverages aggravates postprandial lipemia by dual mechanisms; by an increased *de novo* lipogenesis reflected by increased liver fat content and VLDL production; and by a decrease in the clearance rate of TRLs linked to reduction in LPL activity.

**This project addresses the following specific questions:**

1. Does a diet supplemented with fructose-containing beverages increase postprandial lipemia independently of body weight gain due to extra calories?
2. Does a diet supplemented with fructose-containing beverages increase DNL, VLDL production and liver fat deposition more in high risk HTG obese subjects than in NTG obese individuals?
3. Is the clearance of TRLs in the postprandial state impaired in response to a diet supplemented with fructose containing beverages?
  - A. Is a potential clearance defect of TRLs linked to responses of apo-CIII and apo-A5 to a diet with high fructose?
  - B. Are LPL mass and activity responses different in NTG vs. HTG subjects during fructose diet?
4. Is blood pressure raised by a diet supplemented with fructose-containing beverages?
5. Is the acute inflammatory response to a fructose-rich diet measured in the fasting state or the postprandial period exacerbated in obese subjects with HTG?
6. Do common variants in genes affecting lipid metabolism (individually and/or when combined) modify the effect of a diet enriched in fructose-containing beverages on lipid metabolism (in particular hypertriglyceridemia), and gene expression in adipose tissue?
7. Is gut microbiota modified by a diet enriched in fructose-containing beverages and are these changes linked to metabolic dysfunction?

**Study design, subjects and methods**

This international, multi-center, randomized study has four centers: Helsinki University, Finland; University of Gothenburg, Sweden; Napoli University, Italy; and Laval University, Canada. Each centre enrolls 32 subjects (see footnote below).i Thus, total number of subjects will be  $n=128$  (**Figure 4**).

**Experimental diets**

Subject eligible for the study **will be randomly assigned to one of the two diet groups for 12 weeks:**

**A) "Hypercaloric fructose diet group"**

Subjects will be instructed to drink 990 ml of a beverage sweetened with 7.6 % fructose per day while consuming a self-selected *ad libitum* (usual) diet. No advice is given to reduce the energy content of their usual diet. Subjects will be in positive energy balance and therefore subjected to a weight gain of up to 2.5 kg in the 3 month study period. The subjects will be followed by the trained dietitian 6 weeks after the study to ensure that the subjects return to a BW of maximum 1 kg above their baseline BW.

i Helsinki University plans to perform a kinetic study as an extension of the main study. The aim of the substudy is to elucidate the effects of fructose diet on lipoprotein metabolism using stable isotopes. This substudy replaces study visit 3 and is described on page 9.

### **B) "Isocaloric fructose diet group"**

Subjects will be instructed to drink 990 ml of a beverage sweetened with 7.6 % fructose per day while consuming an isocaloric diet. This group will be instructed by a trained dietitian to reduce their carbohydrate intake from other source by 75 g in order to remain in neutral energy balance. Subjects are required to keep their weight stable during the 3 months and their daily energy intake will be adjusted by the dietitian if the body weight deviates more than 1 kg at the weekly check-ups.

### **Dietary protocol**

The beverages will be prepared as 7.6 % (w/w) solutions flavored with unsweetened drink mix. 750 ml of fructose sweetened beverage provides 75 g of fructose and 304 kcal corresponding to 15 % of energy intake for a person with a daily caloric intake of 2000 kcal. Subjects will be instructed to consume the beverages together with the main meals. During traveling the fructose drink may be replaced by crystalline fructose (75 g, same brand in each center) during weeks 1-10 but not during the last two weeks of fructose consumption for maximum of 5 days during the whole study.

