### **Assessment of dietary intake**

To assess habitual food and beverage consumption, subjects will participate in a baseline evaluation that includes a dietary record on 3 consecutive days including 2 weekdays and 1 weekend day. The subjects will be carefully instructed not to change their usual eating habits. Further, subjects are asked to repeat the 3-day food diaries at week 4, and 11 to obtain a total of 9-day diaries during the intervention period. The mean of the 6-9 days will be used to estimate energy and macronutrient intake from the diet during the intervention period. Participants are not required to weight foods but are asked to measure the volume of foods consumed with household measurements (cups, tablespoons) or to indicate the weight of the products. After completing the food records, participants will meet with the dietitian to review the food records for completeness. Energy and macronutrient intake will be calculated by the dietitian using local dietary programs, which is based on a national Finnish database for food composition. Subjects carry a pedometer during the days of dietary recordings.

Subjects are required to be in contact with the dietitian once per-1-3 weeks to control beverage supply, to monitor weight and compliance. The home scale is checked at the first visit.

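### The Dietary protocol says 750 ml of a 7.6% beverage supplies 75 g of fructose, but that volume holds about 57–59 g, and both arms are told to drink 990 ml

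*Protocol*

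**What the plan says.** Three sections of the Protocol describe the study beverage.

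- **Group A (Hypercaloric fructose diet group):** participants are to "drink 990 ml of a beverage sweetened with 7.6 % fructose per day".
- **Group B (Isocaloric fructose diet group):** the volume and strength are the same ("drink 990 ml of a beverage sweetened with 7.6 % fructose per day while consuming an isocaloric diet"). A dietitian also instructs this group to "reduce their carbohydrate intake from other source by 75 g in order to remain in neutral energy balance".
- **Dietary protocol:** strength and basis are given as "The beverages will be prepared as 7.6 % (w/w) solutions flavored with unsweetened drink mix". The next sentence says that "750 ml of fructose sweetened beverage provides 75 g of fructose and 304 kcal" and equates those 304 kcal with 15% of a 2000 kcal daily intake. Later in the section, 75 g of crystalline fructose is allowed as a limited substitute when travelling.

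Under Assessment of dietary intake, regular contact with the dietitian serves "to control beverage supply, to monitor weight and compliance". No reference volume is given there.

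**The concern.** Two things do not fit. First, the sentence on content does not follow from the strength stated immediately before it: a 7.6% solution has roughly 7.6 g per 100 ml, and 750 ml of it cannot reach 75 g. Second, the sentence ties a day's share of energy to 750 ml, while both groups are told to drink 990 ml per day.

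The beverage is the intervention, and it is to be given in the same way at four centres. The isocaloric arm also depends on the beverage and the carbohydrate reduction cancelling out at 75 g each. If a centre worked from the 750 ml sentence at the stated strength, participants would receive less fructose than planned, and the isocaloric arm would remove more carbohydrate than the drink replaces. A check of beverage supply also needs one unambiguous daily volume.

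**Working it through.** **Inputs from the Protocol**

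- Strength: 7.6% in all three sections. It is stated as w/w in Dietary protocol; no basis is given under groups A and B.
- Volume: 750 ml (Dietary protocol); 990 ml per day (groups A and B).
- Stated content of 750 ml: 75 g, 304 kcal, 15% of 2000 kcal.
- Carbohydrate reduction in group B: 75 g. Travel substitute: 75 g.

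**Assumption.** The Protocol gives no density, so 1.00, 1.03 and 1.04 g/ml are used. Density 1.00 gives the same result as reading 7.6% as weight per volume, so both readings are covered.

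**Step 1: do grams, kcal and energy share agree with one another?**
304 / 75 = 4.05 kcal/g, and 304 / 2000 = 15.2%. They do. The 75 g reduction and the 75 g substitute match as well.

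**Step 2: does 750 ml at 7.6% give the stated content?**
grams = volume × density × 0.076; kcal = grams × 4.053 (that is, 304/75).

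| Density (g/ml) | Fructose in 750 ml | Energy | Share of 2000 kcal | Against 75 g |
|---|---|---|---|---|
| 1.00 | 57.0 g | 231 kcal | 11.6% | −24.0% |
| 1.03 | 58.7 g | 238 kcal | 11.9% | −21.7% |
| 1.04 | 59.3 g | 240 kcal | 12.0% | −21.0% |

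The stated 75 g and 304 kcal are not reproduced under either reading. A rounder factor of 4 kcal/g lowers the energy slightly, to 228–237 kcal.

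**Step 3: what would make the sentence true?**
- Keeping 7.6% and 750 ml, the density would have to be 75 / (750 × 0.076) = 1.32 g/ml, far outside the assumed range.
- Keeping 750 ml and 75 g, the strength would have to be 75 / (750 × density) = 10.0%, 9.7% or 9.6% w/w at densities 1.00, 1.03 and 1.04. No section states such a strength.

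**Step 4: the volume in the group instructions.**
990 × density × 0.076 = 75.2 g, 77.5 g or 78.2 g, which is 305, 314 or 317 kcal. The two volumes differ by 990 − 750 = 240 ml.

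**Step 5: conditional effect on the isocaloric offset.**
Only if 750 ml at 7.6% were dispensed: 75 − 57.0 = 18.0 g, 75 − 58.7 = 16.3 g, 75 − 59.3 = 15.7 g. At 4.053 kcal/g these are 73, 66 and 64 kcal per day by which the carbohydrate reduction would exceed the fructose supplied, before any adjustment by the dietitian.

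**The case against.** The strongest reply is that this is one stray number. The 750 ml appears in one descriptive sentence, and no section tells anyone to drink or dispense that volume. The instructions that participants actually follow appear twice and agree. The preparation strength is the same everywhere, and 990 ml at 7.6% comes to about 75 g at density 1.00, in line with the remaining figures. Both arms receive the same beverage instruction. Neither primary comparison (normotriglyceridemic against hypertriglyceridemic participants, or isocaloric against hypercaloric feeding in the latter) uses the 750 ml figure, and neither do the sample-size assumptions. The shortfall in the isocaloric offset is therefore hypothetical.

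Much of this stands, and it limits how serious the point is. Both discrepancies come from one sentence, the effect on exposure is conditional, and no bias is demonstrated. But the arithmetic error remains even if the 750 ml is only an illustration. Because the sentence expresses the content as a share of daily intake, and the same 75 g recurs as the carbohydrate reduction and the travel substitute, it reads as a daily amount. That a reader can guess how the mismatch arose does not reconcile the text, and the Protocol does not say which volume is meant.

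It is also true that the Assessment of dietary intake section is not itself in error and that there is no evidence of wrong dispensing. Asking the centres is a precaution, not an allegation.

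**Conclusion.** The statement is wrong as written. At the Protocol's own strength, 750 ml holds 57–59 g and 231–240 kcal, a shortfall of 21–24% against the stated 75 g and 304 kcal. The volume also differs by 240 ml from the daily amount set for both groups, and no section reconciles the two. The result rests on an assumed density of 1.00–1.04 g/ml and the Protocol's implied 4.05 kcal/g; no value in that density range rescues the sentence.

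This is an error in the specification of the study exposure. It is not a demonstrated change in what participants received, and the 16–18 g (64–73 kcal) daily gap in the isocaloric arm applies only if 750 ml at 7.6% was dispensed. It should be corrected because it concerns the intervention itself and is tied to the isocaloric arm's offset.

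**What to change.** Reconcile the sections for groups A and B with the Dietary protocol section so that volume, strength, grams and kcal agree with one another, with the carbohydrate reduction and with the crystalline substitute. State in every place whether the strength is by weight or by volume and, if by weight, give the density used. This review does not say which figure is right; the sponsor must settle that.

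Use the reconciled daily volume as the reference for the dietitian's supply check, and ask each of the four centres what volume and strength it prepared and dispensed. If any centre departed from the reconciled specification, record this so that delivered fructose can be described correctly.

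The cost is a wording correction in three short sections and one query per centre. The design, sample size and assessments do not change.

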### **Assessment of dietary intake**

To assess habitual food and beverage consumption, subjects will participate in a baseline evaluation that includes a dietary record on 3 consecutive days including 2 weekdays and 1 weekend day. The subjects will be carefully instructed not to change their usual eating habits. Further, subjects are asked to repeat the 3-day food diaries at week 4, and 11 to obtain a total of 9-day diaries during the intervention period. The mean of the 6-9 days will be used to estimate energy and macronutrient intake from the diet during the intervention period. Participants are not required to weight foods but are asked to measure the volume of foods consumed with household measurements (cups, tablespoons) or to indicate the weight of the products. After completing the food records, participants will meet with the dietitian to review the food records for completeness. Energy and macronutrient intake will be calculated by the dietitian using local dietary programs, which is based on a national Finnish database for food composition. Subjects carry a pedometer during the days of dietary recordings.

Subjects are required to be in contact with the dietitian once per-1-3 weeks to control beverage supply, to monitor weight and compliance. The home scale is checked at the first visit.

### **Power calculations**

Primary endpoints in the current study are 1) change in plasma triglyceride (TG) area under curve (AUC) between the NTG and HTG during fructose feeding (between groups) and 2) change in TG AUC in HTG subjects during isocaloric fructose vs. hypercaloric fructose feeding (within group). The calculations are based on following assumptions: TG AUC increases from 7 to 10.5 mmol/l×hrs in normotriglyceridemic and from 7-9 to 14 mmol/l×hrs in hypertriglyceridemic subjects during fructose. Standard deviation is assumed to be 4.3 based on previous studies in similar groups of patients. 1) To detect significant difference (>3.5 mol/l×hrs) between the groups ( $n=25$ ) with unpaired t-test. 2) To detect significant increase (>3.5 mol/l×hrs) within the group ( $n=15$ ) with paired t-test. These calculations assume that alpha = 0.05 and power = 0.80 in all tests.

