### **Objectives**

This project focuses on the deleterious effects of fructose-containing beverages on lipid metabolism. Our hypothesis is that consumption of fructose-containing beverages increases *de novo* lipogenesis (DNL) with numerous consequences on lipid and glucose metabolism, insulin resistance, inflammation and blood pressure. We further propose that fructose also decreases the removal of triglyceride-rich lipoproteins (TRLs) from the circulation by inhibiting the activity of lipoprotein lipase (LPL), a key enzyme in lipoprotein metabolism. We therefore focus our study on the effects of fructose on postprandial lipemia and features of ectopic fat deposition including visceral adipose tissue and liver fat content which are key features of individuals with metabolic syndrome and type 2 diabetes. So far, little data exist on the pathophysiological responses to fructose-containing beverages in obese subjects with multiple cardiometabolic risk factors. We will test the hypothesis that hypertriglyceridemic (HTG) obese subjects are particularly prone to the deleterious effects of fructose-containing beverages compared to normolipidemic (NTG) obese subjects. We have therefore designed our study to differentiate the weight-dependent vs. weight-independent effects of fructose-rich diet in HTG and NTG obese subjects.

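### No stated primary comparison uses the randomised diet contrast in NTG men, or tests whether that contrast differs between HTG and NTG men, although the objective covers both phenotypes

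*Protocol*

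**What the plan says.** The Objectives section of the protocol gives two aims that bear on this point. The study was "designed our study to differentiate the weight-dependent vs. weight-independent effects of fructose-rich diet in HTG and NTG obese subjects", and it tests whether "hypertriglyceridemic (HTG) obese subjects are particularly prone to the deleterious effects of fructose-containing beverages compared to normolipidemic (NTG) obese subjects". Specific question 1 asks whether the fructose diet will "increase postprandial lipemia independently of body weight gain due to extra calories"; it names no phenotype. Specific question 2 asks about HTG versus NTG and names no diet arm.

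Under Experimental diets, eligible men "will be randomly assigned to one of the two diet groups for 12 weeks". Both groups drink the fructose beverage. One is expected to gain weight; the other is held weight-stable.

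Power calculations fixes two primary endpoints. The first is "change in plasma triglyceride (TG) area under curve (AUC) between the NTG and HTG during fructose feeding (between groups"), sized for a difference "between the groups ( $n=25$ ) with unpaired t-test". The second is "change in TG AUC in HTG subjects during isocaloric fructose vs. hypercaloric fructose feeding (within group"), sized with a paired t-test at n=15. The section states no other primary comparison.

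**The concern.** Two phenotypes and two randomised diets make a 2×2 layout. Diet is the randomised factor; phenotype is observed. Diet is also the only design feature that distinguishes an effect of fructose with weight gain from an effect without it.

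The two primary endpoints cover this layout only in part. The first looks across phenotypes and is silent on diet. The second looks across diets and leaves NTG men out. Two things follow. The randomised diet information in NTG men enters no stated primary comparison. And if the diets differ significantly in HTG men, a reader may conclude that HTG men respond more strongly to excess energy than NTG men do, although no stated test addresses that difference.

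**Working it through.** **Inputs.** From Power calculations: SD 4.3, target 3.5 mmol/l×hrs for both tests, alpha 0.05, power 0.80, n=25 (unpaired) and n=15 (paired). From Study design, subjects and methods: 4 × 32 = 128 men. Assumptions: two-sided tests; n=25 is per group; 4.3 is the SD of the change; HTG and NTG are split evenly. The protocol does not state the split. An even split gives 64 men per phenotype and 32 per phenotype-by-diet cell.

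**Reproducing the plan's figures.**
- Unpaired t-test, standardised difference 3.5/4.3 = 0.814: 24.7 per group, so 25, with power 0.805. The stated 25 reproduces.
- Paired t-test, with 4.3 as the SD of the differences: 13.9, so 14; power at 15 is 0.83. The stated 15 is within one or two men.

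These figures size an HTG-versus-NTG comparison without diet and a before-after change in one group. Neither sizes a comparison between diet arms.

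**Which contrasts are covered.**

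| Contrast | In a stated primary comparison? |
|---|---|
| HTG vs NTG | Yes, no diet arm named |
| Hypercaloric vs isocaloric, HTG men | Yes, but sized with a paired test |
| Hypercaloric vs isocaloric, NTG men | No |
| Diet contrast in HTG minus diet contrast in NTG | No |

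**Diet contrast within one phenotype.** The arms hold different men, so the comparison is unpaired. For a difference of 3.5, power is 0.58 with 15 per arm, 0.81 with 25 and 0.89 with 32.

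**Interaction.** SE = SD × √(4/n), with n per cell. At n=32: 4.3 × √(4/32) = 1.52. The difference detectable at 80% power is about (1.96 + 0.84) × 1.52 ≈ 4.3. Power for 3.5 is 0.63 at 32 per cell, 0.52 at 25 and 0.34 at 15. Reaching 80% power for 3.5 would take 48 per cell, or 192 men.

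If 4.3 is instead a cross-sectional SD, the SD of the change is 4.3 × √(2(1−r)). For before-after correlations r of 0.3 to 0.7 this runs from 5.1 down to 3.3, and interaction power at 32 per cell runs from 0.49 to 0.84.

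**Does ignoring diet hurt the first endpoint?** Suppose the diets differ by 3.5 (an assumption) and are equally represented. The variance becomes 4.3² + 3.5²/4 = 18.49 + 3.06 = 21.55, so the SD is 4.64. At 25 per group, power falls from 0.805 to 0.743. At 64 per phenotype, it falls only from 0.995 to 0.988.

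**The case against.** The case against has several parts, and some of it stands.

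- **Pooling is an inference.** The first endpoint names no arm. Pooling both diets is the natural reading, since both receive fructose, but HTG versus NTG within each arm is also possible, and the layout figure is not available. This stands as a caution. It does not rescue the plan: an HTG-versus-NTG test within an arm does not compare the diets either.
- **An interaction is not promised.** A reader might infer that the Objectives commit the trial to testing whether the energy effect differs by phenotype. The wording fits separate estimates within each phenotype at least as well, and the phenotype hypothesis concerns fructose, not excess energy. This stands. Even on that reading, the diet contrast in NTG men is needed and is missing.
- **Power loss.** A reader might infer that leaving diet out seriously weakens the first endpoint. The fall from 80% to 74% describes 50 men, not 128, and it borrows 3.5 as a diet difference, which the protocol never states. With 64 per phenotype the loss is under one percentage point. The power argument should not be used.
- **Analysis-plan territory.** Model terms and supporting contrasts often sit in an analysis plan, which may exist. But this protocol itself fixes the primary comparisons and names their tests, and these do not match its objective.
- **A primary endpoint may be limited to HTG men.** It may, and the change below keeps it so.

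**Conclusion.** The point holds as a mismatch between the objective and the primary comparisons. The randomised diet contrast in NTG men is in none of them, and a significant result in HTG men alone would not show that the energy or weight effect depends on phenotype. The protocol does not make that claim; the risk is that a reader draws it.

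The second endpoint has a further defect: it compares two parallel randomised arms but is labelled within-group and sized with a paired test. With 15 men per arm, the fitting unpaired test would have power 0.58 for a difference of 3.5.

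The documents do not support saying that the plan breaks a promise to test an interaction, or that the first endpoint loses meaningful power. The figures at 32 per cell and 64 per phenotype rest on an assumed even split, and the power figures take 4.3 as the SD of the change. The mismatch itself rests on neither.

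**What to change.** Replace the two named t-tests with one linear model of change in TG AUC on all randomised men, with terms for phenotype, diet and phenotype-by-diet.

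1. Endpoint 1: the HTG-minus-NTG contrast, averaged equally over the two diets.
2. Endpoint 2: the hypercaloric-versus-isocaloric contrast within HTG men, as a comparison between arms and not a paired test. State its sample size on that basis.
3. Supporting estimates: the diet contrast in NTG men, and the interaction with its confidence interval.
4. State that a phenotype-specific energy effect will be claimed only from the interaction.

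The cost is a few lines of text, with no extra men or visits. The downside is that the interaction will be imprecise: about 4.3 mmol/l×hrs detectable at 80% power, and power of about 0.63 for 3.5, assuming 32 men per cell and SD 4.3. A non-significant interaction should therefore not be read as showing that the two phenotypes respond alike.

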**Studies 2-5 for screen positives are performed twice: before and at the end of the three month diet period.**

### **2. Lipolytic enzymes and genetic studies**

**2.1** Subjects will receive 75 IU/kg heparin *i.v.* to determine lipoprotein lipase and hepatic lipase masses and activities.

**2.2** A blood sample for DNA extraction is drawn. Single nucleotide polymorphisms (SNPs) in genes involved in regulation of lipid metabolism, insulin resistance, inflammation or oxidative stress will be analyzed using Taqman and Sequenom methods. In addition, among hyper- and hyporesponders to fructose, expression quantitative trait loci (eQTL) analysis will be performed comparing mRNA transcript levels and their changes during the intervention from adipose tissue biopsies and relating this to genetic variation.

**2.3** Since diet may lead to low-grade inflammation and insulin resistance due to changes in gut microbial community, the subjects will also provide a stool sample (using specific tubes and instructions) for analysis of gut microbiota profile (future analysis) and answer a health questionnaire. A blood sample for lipopolysaccharide (LPS) and angiopoietin-related protein 4 (Angptl4/fait) analyses is drawn for future analyses.

**2.4** The questionnaire of physical activity is done twice: before fructose period and during weeks 10-12

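### Primary endpoint 2 compares two diets given to different men, but it is sized as a before-after rise with a paired t-test and n=15

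*Protocol*

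**What the plan says.** The Power calculations section lists two primary endpoints. The first compares the change in triglyceride (TG) AUC between normotriglyceridemic (NTG) and hypertriglyceridemic (HTG) men. The second is "change in TG AUC in HTG subjects during isocaloric fructose vs. hypercaloric fructose feeding (within group".

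Item 2 of the sizing then reads: "To detect significant increase (>3.5 mol/l×hrs) within the group ( $n=15$ ) with paired t-test". The section closes with "These calculations assume that alpha = 0.05 and power = 0.80 in all tests". Its AUC assumptions are rises during fructose by lipid group, 7 to 10.5 for NTG and 7–9 to 14 for HTG, with an SD of 4.3. It gives no values by diet.

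On the design, the Experimental diets section says that eligible men "will be randomly assigned to one of the two diet groups for 12 weeks", and sections A and B describe two separate groups. Under Study visits, the schedule states: "Studies 2-5 for screen positives are performed twice: before and at the end of the three month diet period".

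**The concern.** The endpoint names a difference between two diets, while the sizing describes a rise within one group. Because each man follows a single diet, the only pairs in this trial are a man's own values before and after it. A paired test on those pairs asks whether TG AUC rises on a diet. It does not ask whether it rises more on one diet than on the other.

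This matters because NTG versus HTG is not a randomised comparison. Endpoint 2 is thus the only randomised contrast among the primary endpoints. It is also the contrast that serves the aim in the Objectives to "differentiate the weight-dependent vs. weight-independent effects of fructose-rich diet in HTG and NTG obese subjects". If the text stands, the claim of 80% power in all tests covers an endpoint for which no power was derived. The text would also permit separate before-after tests in each arm to be reported in place of the randomised comparison.

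**Working it through.** **Inputs from the protocol.** Rise or difference 3.5 and SD 4.3. The unit is taken as mmol/l×h, as for the AUC assumptions, although the detection thresholds are printed in mol. Alpha is 0.05, power 0.80, n=15 for item 2 and n=25 for item 1. Total enrolment is 128, from four centres: "Each centre enrolls 32 subjects".

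**Assumptions made here.** Tests are two-sided, since sidedness is not stated. Where 32 HTG men per diet is used, the 128 are assumed to split evenly over two lipid groups and two diets (128/4 = 32). That split is not in the text available; it may be in Figure 4, which is not shown.

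**Step 1: reproduce the stated n.** For a paired t-test, the noncentrality is (Δ/SD of change)·√n with n−1 degrees of freedom. With Δ = 3.5 and SD of change = 4.3, Δ/SD = 0.814.
- n = 14: power 80.4%, the smallest n that reaches 80%.
- n = 15: noncentrality 0.814·√15 = 3.15, power 83.4%.

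So n=15 is sound for a before-after rise of 3.5, provided 4.3 is the SD of the change.

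**Step 2: the contrast that endpoint 2 names.** For two independent groups compared on change, the noncentrality is (Δ/SD of change)·√(n/2) with 2n−2 degrees of freedom, n per arm. Borrowing 3.5 as the difference between diets and 4.3 as the SD of change:

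| HTG men per diet arm | Noncentrality | Power |
|---|---|---|
| 15 | 2.23 | 58% |
| 24 | 2.82 | 79% |
| 25 | 2.88 | 80% |
| 32 | 3.26 | 89% |

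The 25 per arm equals the n=25 that the protocol gives for item 1, where it does use an unpaired test. The method for independent groups was available in the same paragraph and was not applied to endpoint 2.

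**Step 3: how far the answer depends on what is not stated.** These are illustrations.

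If 4.3 is the SD of a single AUC, the SD of change is 4.3·√(2(1−r)), where r is the before-after correlation. With a difference of 3.5:

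| r | SD of change | n per arm for 80% | Power at 32 per arm |
|---|---|---|---|
| 0 | 6.08 | 49 | 62% |
| 0.25 | 5.27 | 37 | 74% |
| 0.5 | 4.30 | 25 | 89% |
| 0.75 | 3.04 | 13 | over 99% |

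If 4.3 is the SD of change but the diets differ by another amount:

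| Difference between diets | n per arm for 80% | Power at 32 per arm |
|---|---|---|
| 2 | 74 | 45% |
| 2.5 | 48 | 63% |
| 3 | 34 | 78% |
| 3.5 | 25 | 89% |
| 5 | 13 | over 99% |

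Both arms drink the same fructose beverage, and 3.5 is the whole before-after rise assumed for NTG men (10.5 − 7). It cannot be carried over as the difference between diets without a reason.

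**The case against.** The strongest reply is that item 2 is coherent as a before-after calculation. An increase, within the group, "with paired t-test" and n=15 all fit together, and the endpoint itself carries the label within group. Specific question 1 asks whether fructose raises postprandial lipemia independently of weight gain, and a rise in the weight-stable isocaloric arm would speak to that. On this reading the misplaced words are the ones naming the two diets. Alternatively, within group may mean within the HTG stratum.

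The first reading moves the error without removing it. The endpoint as written compares two diets, so either its wording or its sizing is wrong. The second reading rescues the label but not the test, because the two diets still go to different HTG men.

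It can also be said that total enrolment is probably adequate: the item 1 inputs would need 25 per arm, and an even split gives 32. That stands as far as it goes, and it is why no claim of underpowering is made. It still depends on a difference between diets that the protocol never states. The planned number per cell may be in Figure 4, so its absence from the text is not counted as a fault. The choice of analysis model can be left to the statistical analysis plan; a test and n stated in the protocol for the wrong contrast cannot.

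**Conclusion.** The concern holds. The test, n and power given for item 2 belong to a before-after rise (83% at n=15), not to the comparison of isocaloric with hypercaloric fructose that the endpoint names. With the protocol's own 3.5 and 4.3 borrowed for that comparison, 15 per arm gives 58% and 25 per arm are needed. These figures assume a two-sided test and that 4.3 is the SD of the change.

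The fault lies in the stated justification. The trial is not shown to be too small: 32 per arm would give 89% under the same assumptions, but 63% if the diets differ by 2.5. The contradiction is certain; the true power for endpoint 2 cannot be given from the inputs stated. It should be fixed because it concerns the only randomised primary contrast.

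**What to change.** In the Power calculations section:

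1. State endpoint 2 as the difference between arms (hypercaloric minus isocaloric) in change in TG AUC among HTG men.
2. Replace the paired t-test in item 2 with a comparison of changes between independent groups, or an analysis of covariance adjusting for baseline AUC.
3. Replace n=15 with the planned number of HTG men per diet arm, the assumed difference between diets, the SD of the change (or the SD of one AUC with the before-after correlation) and the resulting power.
4. List any before-after analysis within an arm as a separate item with its own n.

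If a before-after endpoint was in fact intended, the endpoint wording must change instead, and the protocol should then say that neither primary endpoint is a randomised comparison.

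The cost is rewording one section and restating its assumptions. No change in enrolment is shown to be needed.
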